1.2 Rationale of the Study

Preeclampsia is a hypertensive disorder specific to pregnancy that remains a significant cause of maternal & neonatal morbidity & mortality. Because of the potential negative health consequences of PE for women & newborns & the lack of effective screening mechanisms, preventing PE is an important component of prenatal care. Bangladesh Maternal Mortality survey(BMMS) 2010 revealed that eclampsia is the second most common direct cause of maternal death in Bangladesh followed by PPH.Among 5000 to 6000 maternal deaths each year,1000 to 1,200 are due to Eclampsia.(Landscape report,2015). Preeclampsia should be detected and appropriately managed before the onset of convulsions (eclampsia) and other life-threatening complications.

Since there is no curative treatment other than delivery, an intervention that could prevent preeclampsia would have a significant impact on maternal and infant health worldwide. Researchers have documented that low dose aspirin during antenatal check- up can prevent the development of PE who are at high risk of developing PE and also reduce the incidence of pre-term birth & fetal growth restriction. The relevant evidence of Asian women is very limited. Its safety is sometimes questionable. BIRDEM is a center of excellence where majority patients are diabetic and so many high risk for developing PE. Therefore, this study has been designed to evaluate the role of aspirin in reducing the incidence of preeclampsia including its dose and duration of use & safety of the drug.

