1.4 Objectives

General objective

- To find out the effect of low dose aspirin in prevention of preeclampsia among pregnant women who are at high risk for developing preeclampsia.

Specific objectives

- To find out the socio-demographic characteristics (Age, Occupation,
- To find out the primary outcome (occurrence of Preeclampsia) among both intervention & control group.
- To detect the secondary outcome among both groups: Maternal- Gestational HTN, Oligohydramnios, Preterm labor, Placental abruption, APH, PPH ; Fetal- LBW, Preterm birth , Small for gestational age, IUD,Still Birth, NICU admission among both groups.
- To compare the outcome of two groups.
- To analyze the possible association between Aspirin & Pre-eclampsia.

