3.5 Sampling technique

Simple randomization through lottery in a closed envelope. Randomization number will determine who will receive aspirin & who will not receive aspirin.

2.6 Study Procedure :

This Randomized clinical trial will be conducted in BIRDEM-II. Approval from Institutional Review Board will be taken. The study population will be pregnant women with risk factors for developing PE attending department of Obstetrics and Gynecology, BIRDEM-II. Pregnancy will be confirmed via USG. Then evaluation of risk factors of PE will be done by history taking, examinations & provided investigations. Those who will be eligible according to inclusion & exclusion criteria will be enrolled in the study. Trial information will be provided verbally & with a written information sheet. Participants will be randomized by lottery in a closed envelope, which will determine who receive aspirin daily & who will not. A total of 200 women will be included in the study, of whom 100 pregnant women having risk factors of developing pre-eclampsia will be in experimental group & another 100 pregnant women having risk factors for developing PE will be in control group. Experimental group will be prescribed to take 75 mg Aspirin daily after lunch from 12-19 weeks of pregnancy. Control group will not be prescribed to take Aspirin. For each and every subject separate data collection sheet will be prepared. Data will be collected from the patients using the structured design by history, clinical examination, urine & haematological investigations, USG of the patients. Both group of patients will get the usual advices & medications of pregnancy. All patients will be followed up at 19-24 weeks, 32-34 weeks of gestation, 36 weeks of gestation and weekly up to delivery. During follow up SBP & DBP will be carefully measured. Urine analysis will be done. Aspirin will be stopped either 36 weeks of pregnancy or when delivery occurs or when PE is diagnosed. Primary & Secondary outcome will be observed in both experimental & control group separately. Then analysis will be done by comparison of outcome of this two groups. Data will be analyzed using SPSS software.

2.7 Sample size determination:

Sample size is calculated using the following formula

$$n = \left[\frac{Z_{\alpha} \sqrt{p_1(1-p_1)} + Z_{\beta} \sqrt{p_2(1-p_2)}}{p_2 - p_1} \right]^2$$

Here, n= sample size

$p_1 = 1.6\%$ [Incidence of preeclampsia in experimental group (Rolnik et al., 2017)]

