2.11 Research instruments

Structured questionnaire will be prepared for this purpose, which will include all the variables of interests.

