2.13 Data presentation and analysis plan

- Statistical analyses will be carried out by using Windows based Statistical Package for Social Sciences (SPSS-22.0).
- For continuous variables, distributions will be expressed by mean and standard deviation. Mean comparisons between two groups will be done by student's t-test.
- For qualitative variables, distributions will be expressed by frequency and their percentages. Chi square tests will be done to see the significance of differences between two groups.
- Relative Risk (RR) and 95% confidence interval will also be estimated for the outcome.
- The p value <0.05 will be declared as statistically significant.

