2.16 Ethical Consideration

There is minimum physical, psychological, social and legal risk during taking history, physical examination and investigations. Proper safety measures will be taken in every step of the study. Only researcher will be allowed to access the collected data. Ethical clearance will be obtained from Institutional Review Board (IRB) of BIRDEM to undertake the current study. According to Helsinki Declaration for Medical Research involving Human Subjects 1964, all the patients will be informed about the study design, the underlying hypothesis and the right of the participants to withdraw themselves from the research at any time, for any reason. Informed written consent will be obtained from each subject who will voluntarily provide consent to participate in this study.

[figure not shown]
The following ethical issues will be addressed accordingly:

1. Strict confidentiality and security of data related to patient will be maintained. The presentation of data and information related to patient will be documented anonymously.
2. The data analysis will be completed on the subjects who complete the study according to protocol after recruitment of subjects with valid informed consent.
3. There is no additional risk or safety concern due to the research process to either patient or researcher.
4. There is no potential conflict of interest in this study and an entirely an academic research project.

[figure not shown]
Procedure of maintaining confidentiality

1. For safeguarding confidentiality and protecting anonymity each of the patients will be given a special ID number which will be followed during examination and each and every step of the procedure.
2. A signed informed consent will be taken from the patient convincing that privacy of the patient will be maintained.
3. A data collection sheet will be enclosed for which a short interview will be required.
4. No experimental new drug will be administered.
5. No placebo will be used here.

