--------------------	--------	---------------	---------------	---------

3)Education :Illiterate/Primary/SSC/HSC/Graduate/Postgraduate

Obstetric history

Married for

Para

Gravida

ALC

Number of foetus in present pregnancy Singleton / Multiple fetuses

Method of conception- Spontaneous/ OID/ ART

Previous history of Gestational HTN/ PE/ Eclampsia

Previous history of IUGR/ IUD/Still birth

Menstrual History

Cycle Regular/irregular

LMP

EDD

Family history : HTN/PE/Gestational HTN

Medical history: GDM /DM/Chronic

HTN/Hypothyroidism/APS/SLE

Drug history:

Hypersensitivity to Aspirin : Present /Absent

Levothyroxine sodium

Insulin

Others

Antenatal care Regular/Irregular

Clinical examination related informations

PHYSICAL EXAMINATION:

Date					
Height					
Weight					
BMI					
Anaemia					
Jaundice					
Edema					

Date					
Pulse (bpm)					
SBP (mmhg)					
DBP(mmhg)					
Proteinuria					

Proteinuria : trace, 1=+, 2=++, 3=+++ / Nil

Morning urine sample

Per abdominal examination:

Date					
Maturity					
SFH (cm)					
FM					
FHR					

During Follow up:

Complications :

Maternal- No complication/GIT upset / Gestational HTN /APH /oligohydramnios /

Preterm labour/others

Fetal- No complication /SGA/IUGR/IUD/PTB/others

Investigations :

Blood group & Rh typing

CBC

Urine R/M/E

Blood Sugar profile

HBsAg

VDRL

TSH

USG of pregnancy profile:

Mode of delivery: NVD/Caesarean section at weeks of gestation.

Outcome

Maternal: normal

PE - occurred /Not occurred

Gestational HTN

Oligohydramnios

PTL

APH

PPH

Fetal- Sex- weight- kg (Normal/SGA/LGA)

APGAR Score

PTB

NICU admission

IUD/ still birth

Others-

Date :

Signature of the investigator:

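### The completers-only rule in Protocol 2.16 can drop aspirin women who stop for GIT upset or non-delivering early APH, with no counterpart in the untreated control arm

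*Protocol*

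**What the plan says.** - **Analysis set.** Protocol 2.16, item 2 in the list of ethical issues: "The data analysis will be completed on the subjects who complete the study according to protocol". The visible text does not define what counts as completing in that sense.
- **End of treatment.** Protocol 2.6: "Aspirin will be stopped either 36 weeks of pregnancy or when delivery occurs or when PE is diagnosed". A side effect is not on this list.
- **Control arm.** Controls are not prescribed aspirin (2.4, 2.6), and 2.16 adds: "No placebo will be used here".
- **Purpose.** Protocol 1.2 says the study is designed to "evaluate the role of aspirin in reducing the incidence of preeclampsia including its dose and duration of use & safety of the drug".
- **Harms collected.** The data collection sheet has, for follow-up complications, "Maternal- No complication/GIT upset / Gestational HTN /APH /oligohydramnios". The maternal secondary outcomes in 1.4 are "Maternal- Gestational HTN, Oligohydramnios, Preterm labor, Placental abruption, APH, PPH".
- **Methods.** Section 2.13 compares categorical variables between arms by chi square and gives a relative risk with its 95% CI. It names no analysis set.

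**The concern.** The rule in 2.16 is the only statement in the visible protocol about who is analysed. It is a positive rule, so this is more than a detail left to a statistical analysis plan: a plan that analysed everyone randomised would have to depart from it.

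Read together with 2.6, the rule makes staying in the analysis depend on tolerating the drug. A woman who gives up aspirin because it upsets her stomach, or because she bleeds before 36 weeks without delivering, has stopped for a reason that 2.6 does not list. If she is then left out, her event leaves the aspirin numerator. A control woman with the same complaint has nothing to stop and stays in. Controls can be lost for other reasons, such as withdrawing or taking aspirin on their own account, but not for this one.

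The study names drug safety among its purposes. A comparison that filters out part of the intolerance in one arm would, by that filter alone, make aspirin look better tolerated than it is.

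**Working it through.** The plan states no figure for side effects, bleeding or stopping, so there is nothing of its own to reproduce. What can be shown is the direction of the effect and how sensitive the relative risk is.

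**Step 1: which events can trigger the exclusion.** The event must make a woman stop aspirin at a time and for a reason outside 2.6.

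| Event | Can it cause a stop outside 2.6? |
|---|---|
| GIT upset before 36 weeks | Yes |
| APH before 36 weeks, no delivery | Yes |
| APH leading to delivery, or after 36 weeks | No: delivery is a listed reason, or aspirin has already ended |
| PPH | No: it follows delivery |
| Abruption, IUD or stillbirth ending the pregnancy | No: covered by delivery |

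The event-tied mechanism therefore concerns the first two rows. The other outcomes can be lost only incidentally, for a woman already excluded for stopping aspirin.

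**Step 2: direction.** Let a be the affected women among 100 on aspirin, c those among 100 controls, and k the affected aspirin women who are dropped from numerator and denominator:

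RR = [(a − k)/(100 − k)] / (c/100)

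Compared with a/100, the aspirin proportion falls whenever k > 0 and a < 100, because 100(a − k) − a(100 − k) = −k(100 − a) < 0. The direction does not depend on the rates assumed.

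**Step 3: size under assumed counts.** The 100 per arm is from 2.7; a, c and k are assumptions. The 95% CI is log-Wald, with SE of ln RR = √[1/(a−k) − 1/(100−k) + 1/c − 1/100].

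| Assumed outcome, aspirin vs control | k | Aspirin analysed | RR (95% CI) |
|---|---|---|---|
| GIT upset 10 vs 5 | 0 | 10/100 | 2.00 (0.71 to 5.64) |
| | 2 | 8/98 | 1.63 (0.55 to 4.82) |
| | 5 | 5/95 | 1.05 (0.31 to 3.52) |
| GIT upset 5 vs 5 | 0 | 5/100 | 1.00 (0.30 to 3.35) |
| | 2 | 3/98 | 0.61 (0.15 to 2.49) |
| APH 6 vs 4 | 0 | 6/100 | 1.50 (0.44 to 5.15) |
| | 2 | 4/98 | 1.02 (0.26 to 3.97) |

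The APH rows assume that the two dropped cases occurred before 36 weeks and did not lead to delivery.

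**Step 4: the opposing bias.** Women who know they take aspirin may report GIT upset more readily. With m over-reports on aspirin, the numerator becomes a + m − k. For 10 vs 5:

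- m = 2, k = 0: (12/100)/(5/100) = 2.40 (0.88 to 6.56).
- m = 2, k = 2: (10/98)/(5/100) = 2.04 (0.72 to 5.76).

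The two biases cancel when (a + m − k)/(100 − k) = a/100, that is m = k(1 − a/100). With a = 10, this is 2 × 0.9 = 1.8 over-reports for k = 2 and 5 × 0.9 = 4.5 for k = 5.

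**The case against.** **The phrase may not mean this.** It is undefined, it stands in a list of ethical issues and not in 2.13, and the rest of the sentence is about consent. The sentence in 2.6 can be taken as the planned duration of treatment, not as a list whose breach removes a woman from the analysis. If completing means only being followed to delivery, women who stop aspirin stay in and no bias arises. This stands as a limit. It does not dispose of the point, because the reference to the protocol seems to ask for more than attendance, and in an open-label trial its meaning should not be settled after arm and outcome are known.

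**The diagrams are not visible.** Sections 2.17 and 2.18 survive only as headings in the text at hand. A CONSORT diagram is a usual place to show discontinuations and numbers analysed. A reader might infer that the protocol has no other analysis set at all; that can be said only of the visible text.

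**Stopping may be rare.** The 75 mg dose, taking it on a full stomach (2.4) and the exclusion of peptic ulcer disease (2.8) all make GI stopping less likely. This stands: k may be small or zero.

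**Safety is not an objective.** The word is missing from the hypothesis and from 1.4. But 1.2 makes it a purpose, and 1.4 lists bleeding outcomes. Conversely, a reader might infer that GIT upset would go unanalysed because 1.4 omits it. The documents do not support that: the sheet records it in both arms, and under 2.13 "Chi square tests will be done to see the significance of differences between two groups".

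**Conclusion.** The point holds as a minor one, conditional on the reading of 2.16. If adherence to the aspirin schedule is part of completing, the rule removes women from the aspirin arm only, because of GIT upset or non-delivering APH before 36 weeks, and understates those harms on aspirin. The direction of this exclusion follows from the arithmetic; its size rests entirely on assumed counts. The intervals are wide and include 1 in every scenario, so the effect is on the point estimate and not on a likely change of significance.

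Two stronger readings are not supported. One is that the final safety comparison will favour aspirin: over-reporting in an open-label arm may push GIT upset the other way, so the net bias is unknown. The other is that all listed harms are filtered in the same way: PPH, abruption, IUD and stillbirth do not cause a stop outside 2.6.

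The same rule also governs the preeclampsia comparison, whose bias is not assessed here.

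**What to change.** Amend 2.16, item 2, along these lines: outcomes, including GIT upset and APH, will be compared by assigned arm in all randomised women with follow-up data, whether or not aspirin was stopped; any analysis restricted to completers will be secondary. If the secondary analysis is kept, define in the same place what completing means and whether stopping aspirin for a side effect breaches it.

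For GIT upset, count each woman once if she reports it at any follow-up visit, and give counts, RR and 95% CI by arm. The sheet already collects what is needed, and 1.4 need not change to remove the bias.

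The cost is small: one or two sentences, one table, and continued follow-up of women who stop aspirin. The change does not remove open-label reporting bias in GIT upset, so that caveat must accompany the result.

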--------------------	--------	---------------	---------------	---------

3)Education :Illiterate/Primary/SSC/HSC/Graduate/Postgraduate

Obstetric history

Married for

Para

Gravida

ALC

Number of foetus in present pregnancy Singleton / Multiple fetuses

Method of conception- Spontaneous/ OID/ ART

Previous history of Gestational HTN/ PE/ Eclampsia

Previous history of IUGR/ IUD/Still birth

Menstrual History

Cycle Regular/irregular

LMP

EDD

Family history : HTN/PE/Gestational HTN

Medical history: GDM /DM/Chronic

HTN/Hypothyroidism/APS/SLE

Drug history:

Hypersensitivity to Aspirin : Present /Absent

Levothyroxine sodium

Insulin

Others

Antenatal care Regular/Irregular

Clinical examination related informations

PHYSICAL EXAMINATION:

Date					
Height					
Weight					
BMI					
Anaemia					
Jaundice					
Edema					

Date					
Pulse (bpm)					
SBP (mmhg)					
DBP(mmhg)					
Proteinuria					

Proteinuria : trace, 1=+, 2=++, 3=+++ / Nil

Morning urine sample

Per abdominal examination:

Date					
Maturity					
SFH (cm)					
FM					
FHR					

During Follow up:

Complications :

Maternal- No complication/GIT upset / Gestational HTN /APH /oligohydramnios /

Preterm labour/others

Fetal- No complication /SGA/IUGR/IUD/PTB/others

Investigations :

Blood group & Rh typing

CBC

Urine R/M/E

Blood Sugar profile

HBsAg

VDRL

TSH

USG of pregnancy profile:

Mode of delivery: NVD/Caesarean section at weeks of gestation.

Outcome

Maternal: normal

PE - occurred /Not occurred

Gestational HTN

Oligohydramnios

PTL

APH

PPH

Fetal- Sex- weight- kg (Normal/SGA/LGA)

APGAR Score

PTB

NICU admission

IUD/ still birth

Others-

Date :

Signature of the investigator:

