$p_2 = 8.71\%$ [Incidence of preeclampsia high risk group(Poon L.C et.al., 2019)]

$$p = \frac{p_1 + p_2}{2} = \frac{0.016 + 0.0871}{2} = 5.155\%$$

$Z_{\alpha} = 1.96$ at a 95% confidence interval

$Z_{\beta} = 0.84$ at a 80% power

Putting the values in the above equation the sample size n is estimates as

$$n = \left[\frac{1.96 \sqrt{0.016(1-0.016)} + 0.84 \sqrt{0.0871(1-0.0871)}}{0.0871 - 0.016} \right]^2 = 150.30 \approx 150$$

According to sample size determination it will be 150 in each group but 100 sample size in each group will be taken due to limitation of time.

2.8 Selection Criteria-Pregnant women have to fulfill any 1 of the following criteria to enroll the study

Inclusion criteria for both groups:

- Maternal age ≥ 18 years
- Advanced maternal age (≥ 35 years)
- BMI ≥ 30 kg/m²
- Live foetus at gestational age 12 weeks - 19 weeks.
- Pregnancy interval >10 years.
- Multiple pregnancy.
- Pregnancy assisted by Ovulation inducing drugs/ In vitro fertilization.
- Pregnant women with medical disorders-Chronic HTN,Hyperglycaemia in pregnancy,Thyroid disorder ,Autoimmune disease-APS,SLE.
- Previous history of Gestational HTN,PE, Eclampsia
- Previous history of IUGR, IUD, Still Birth.
- Family history of HTN, Gestational HTN, PE (mother and/or sister)

Exclusion criteria for both groups:

- Allergic to Aspirin.
- Peptic ulcer disease.
- Mental disease.
- Patient with treatment of antifolate drugs (antiepileptics, methotrexate)
- Patient who will not give consent to participate.

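### Multiple pregnancies are eligible, but the data sheet has one birth-weight and size line per woman, so a second baby's low-birth-weight and SGA status at delivery has no field

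*Protocol*

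**What the plan says.** **Eligibility.** Section 2.8 requires any one of the listed criteria, and "Multiple pregnancy" is one of them. No exclusion criterion removes twins.

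**Unit of data collection.** Section 2.6 enrols 200 women, 100 per group, and states: "For each and every subject separate data collection sheet will be prepared".

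**The sheet (Appendices).** Plurality is recorded early on, as "Number of foetus in present pregnancy Singleton / Multiple fetuses", so multiples were foreseen. The Outcome part then gives one fetal line, "Fetal- Sex- weight- kg (Normal/SGA/LGA", followed by one line each for Apgar score, preterm birth, NICU admission and IUD/still birth, and an open line for other findings. The follow-up part has one fetal complications line whose options include SGA, IUD and preterm birth.

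**Use of these fields.** Section 1.4 names as secondary outcomes "Fetal- LBW, Preterm birth , Small for gestational age, IUD,Still Birth, NICU admission among both groups". For qualitative variables section 2.13 says: "Chi square tests will be done to see the significance of differences between two groups". It adds a relative risk with a 95% confidence interval.

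**Blinding.** Section 2.16 says that no placebo is used, and the sheet carries the group label at its head.

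**The concern.** LBW has no tick of its own on the sheet. It has to be derived from the recorded weight, and there is room for one weight. The size class at delivery sits on the same line. If only one of two twins is small, whether the pregnancy counts as affected depends on which baby was written down.

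Two things are at stake. First, affected pregnancies are under-counted for outcomes that the protocol intends to compare between groups. Second, the choice of baby is open to whoever completes the sheet, and that person knows the arm. The documents do not show that this would differ between arms, but nothing prevents it. A second baby's weight that is never written down cannot be recovered at analysis, so a separate statistical analysis plan could not repair this.

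**Working it through.** The plan gives no figure on this point, so there is none to reproduce. It states no twin share, no fetal event rates and no within-pair correlation. The values below are assumptions, shown as a range.

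**Which fields can hold two babies**

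| Section 1.4 outcome | Where the sheet records it | Can one entry serve a twin pregnancy? |
|---|---|---|
| LBW | Derived from the single weight | No |
| SGA | Size class on the same line; also an option on the follow-up complications line | Not at delivery; possible at follow-up |
| Preterm birth | Single tick | Yes |
| NICU admission | Single tick | Yes, if read as any baby; not stated |
| IUD, still birth | Single tick | Yes, if read as any baby; not stated |

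**How many affected pregnancies one record misses**

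Assumed inputs: twin share f = 5% to 20%; event rate in singletons s = 15% to 20%; event rate per twin p with within-pair correlation c, either p = 0.5 with c = 0.5 or p = 0.6 with c = 0.7. The recorded baby is taken to be chosen without regard to outcome.

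- P(both affected) = c·p + (1 − c)·p²
- P(at least one affected) = 2p − P(both)
- Missed per twin pregnancy = P(at least one) − p

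| | p = 0.5, c = 0.5 | p = 0.6, c = 0.7 |
|---|---|---|
| P(both) | 0.25 + 0.125 = 0.375 | 0.42 + 0.108 = 0.528 |
| P(at least one) | 1.0 − 0.375 = 0.625 | 1.2 − 0.528 = 0.672 |
| Missed per twin pregnancy | 0.625 − 0.5 = 0.125 | 0.672 − 0.6 = 0.072 |
| Share of affected twin pregnancies | 0.125/0.625 = 20% | 0.072/0.672 = 11% |

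Per 100 women in an arm:

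- Low end (f = 5%, s = 20%, p = 0.6, c = 0.7): affected = 95 × 0.20 + 5 × 0.672 = 22.36; missed = 5 × 0.072 = 0.36; share = 1.6%.
- High end (f = 20%, s = 15%, p = 0.5, c = 0.5): affected = 80 × 0.15 + 20 × 0.625 = 24.5; missed = 20 × 0.125 = 2.5; share = 10%.

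So about 0.4 to 2.5 women per 100 per arm would be misclassified. If the choice does depend on outcome, the missed number runs from zero (the affected baby of a discordant pair is always recorded) to twice these values (the unaffected one always is).

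**What would happen if babies were entered as subjects**

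The protocol does not say this would be done, so this part is conditional. At equal event rates the design effect is 1 + ICC × (Σm²/Σm − 1), where m is the number of babies per woman, and the actual error rate is 2 × [1 − Φ(1.96/√design effect)]. With 10% twins, Σm²/Σm = (0.9 + 0.4)/1.1 = 1.182. An ICC of 0.5 then gives a design effect of 1.091 and an error rate of 6.1% against the nominal 5%. Over ICC 0.3 to 1.0 the range is 5.3% to 6.1% with 5% twins and 6.2% to 9.0% with 20% twins.

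A simulation (200,000 trials per setting, 100 women per arm, no treatment effect) with event rates of 60% per twin and 20% in singletons, and concordance 0.5 to 1.0, gave 6.7% to 7.5% with 5% twins and 8.4% to 10.7% with 20% twins. Counting each woman once, as affected if any baby is, gave 4.9% to 5.2% in every setting with twins.

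**The case against.** The strongest reply is that the protocol is built around the woman: 200 women, one sheet each, single outcome ticks. Completed as designed, the sheet gives one record per woman, and a chi-square test on those records is valid. This stands. A reader might infer from the single fetal block and the chi-square plan that the false-positive rate is inflated, perhaps to 10%. The documents do not support that: someone would have to add records that the protocol does not provide for, and the upper figures need a 20% twin share and event rates three times higher in twins, neither of which the documents give.

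A reader might also infer that every fetal outcome goes wrong however the form is completed. That is not supported either. Preterm birth, NICU admission and IUD/still birth can be ticked when any baby is affected, which is a sound per-woman definition, and the follow-up line can take SGA in the same way. The gap that remains is in weight, size class at delivery and Apgar score. LBW is the one section 1.4 outcome that rests wholly on it.

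It can also be said that the unit of analysis belongs in a statistical analysis plan, which is not shown. That is fair, and the silence of section 2.13 on the unit is not counted here as a fault. It does not answer the capture problem.

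Finally, staff could write a second baby in the margin or on the open line, and the form's original layout cannot be confirmed from flattened text. Both are possible. But no instruction asks for a second entry, and the form's dated examination tables came through with repeated columns while the Outcome part shows none.

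**Conclusion.** The point holds as a gap in data capture for secondary fetal outcomes, chiefly LBW and size class at delivery. Multiple pregnancies are eligible, the sheet has one weight line, and nothing says which baby goes on it. For NICU admission, preterm birth and IUD/still birth the gap is only a missing instruction that the tick means any baby. Preeclampsia, the primary outcome, is counted per woman and is unaffected.

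The size is modest: about 1.6% to 10% of all affected pregnancies missed. This rests on the assumed twin shares, event rates and correlations, and on a choice of baby unrelated to outcome. No bias between arms has been shown. The open-label design only means that the choice is made with the arm known. The type I error figures are a warning against one way of analysing the data, not a description of what the protocol plans.

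**What to change.** On the data sheet, repeat the fetal outcome block (sex, weight, size class, Apgar, NICU admission, IUD/still birth) once per baby, labelled by birth order.

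In section 2.13, or in the statistical analysis plan if it does not already say so, define each fetal outcome per randomised woman: affected if at least one baby is affected, with the number of randomised women as the denominator. List twins' individual outcomes descriptively. Section 2.16 limits the analysis to women who complete the study according to protocol. That is a separate question, but the denominator has to be reconciled with it.

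The cost is one repeated block and one sentence, with no extra women, visits or tests. The comparison loses some per-baby detail, which the descriptive listing retains. The form change has to be made before outcomes are recorded.
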